**Table 12: Best Overall Radiological Response When Confirmation of CR and PR Required**

Overall radiological response first time point	Overall radiological response subsequent time point	Best overall response
CR	CR	CR
CR	PR	SD, PD or PR a
CR	SD	SD or PD
CR	PD	SD or PD
CR	NE	SD or NE
PR	CR	PR
PR	PR	PR
PR	SD	SD
PR	PD	SD or PD
PR	NE	SD or NE
NE	NE	NE

CR = complete response; NE = not evaluable; PD = progressive disease; PR = partial response; SD = stable disease.

a If a CR is truly met at first time point, then any disease seen at subsequent time point, even disease meeting PR criteria relative to baseline, makes the disease PD at that point (since disease must have reappeared after CR). Best response would depend on whether minimum duration for SD was met. However, sometimes ‘CR’ may be claimed when subsequent scan suggest small lesions were likely still present and in fact the participant had PR, not CR at the first time point. Under these circumstances, the original CR should be changed to PR and the best response is PR.

**4.9.6 Radiological progression.**

The analysis of radiological progression will be based on tumor assessments using RECIST 1.1 (soft tissue) and PCWG3 (bone) criteria.

Participants who have not progressed (i.e., who have a CR, PR, or SD by RECIST 1.1, and non-progressive for bone disease by PCWG3) at the time of analysis will be censored at the time of the latest date of their last evaluable RECIST assessment or bone scan assessment that showed fewer than 2 new lesions.

However, if the two or more consecutive scheduled radiological assessments immediately prior to progression or death were missing, the participant will be censored at the time of the latest evaluable RECIST 1.1 and bone scan assessment prior to the two or more missed assessments. (Note: NE visit is not considered as missed visit).

If the participant has no evaluable visits or does not have baseline data, he will be censored at Day 1 unless he dies within two visits of baseline (in which case the participant’s date of death will be used). The rPFS time will always be derived based on scan/assessment dates, not visit dates.

When the investigator is in doubt as to whether PD has occurred and therefore reassesses the participant at a later date, the date of the initial scan should be declared as the date of progression if the repeat scans confirm progression.

The requirements for determination and confirmation of radiographic progression by either bone scan (bone progression) or CT/MRI (soft tissue progression) are summarised in [Table 13](#).

**Table 13 : Requirements for Documentation of Progression**

Visit Date	Criteria for Bone Progression	Criteria for Soft Tissue Progression
First visit after Baseline (expected week 8)	Two or more new lesions compared to baseline bone scan.  Requires confirmation at least six weeks later with >2 additional lesions compared to the first scan after baseline	Progressive disease on CT or MRI by RECIST 1.1  No confirmation required.
From the 2nd visit after Baseline	Two or more new lesions compared to the first bone scan after baseline.  Requires confirmation at least six weeks later for persistence or increase in number of lesions.	Progressive disease on CT or MRI by RECIST 1.1.  No confirmation required.

**4.9.7 CTC count conversion**

Conversion of CTC count is defined as a change from unfavourable at baseline (CTC  $\geq 5/7.5$  mL blood) to favourable at post-baseline (CTC  $< 5/7.5$  mL blood) (as per PCWG3 criteria) prior to radiological progression. Post-baseline result will be confirmed with a second consecutive value obtained three or more weeks later.

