**4.9.9 Composite response**

Composite response will be defined on the basis of the following outcomes; if any of these occur in the absence of radiological or PSA progression (according to RECIST 1.1 for soft tissue and visceral

lesions, PCWG3 criteria for bone lesions, and PSA) participants will be considered to have responded:

- Investigator assessed radiological objective response by RECIST 1.1 for soft tissue and visceral lesions and PCWG3 criteria for bone lesions. Response must be confirmed at least 4 weeks later. Blinded Independent Central Review (BICR) assessment may be introduced if the cohort is expanded, subject to a protocol amendment.
- Conversion of CTC count from  $\geq 5/7.5\text{mL}$  blood (unfavourable) at baseline to  $< 5/7.5\text{mL}$  blood (favourable) (as per PCWG3 criteria) confirmed by a second consecutive value obtained 3 or more weeks later.
- PSA decline of  $\geq 50\%$  confirmed by a second consecutive measurement at least 3 weeks later (based on PCWG1 criteria).

For visits with non-evaluable radiological response, absence of radiological progression for that specific visit can be decided if there is any subsequent evaluable non progression response (CR/PR/SD). For visits with missing PSA assessment, absence of PSA progression for that specific visit can be decided if there is any subsequent non progressive PSA assessment available. Participants who discontinue study treatment without progression, receive a subsequent anti-cancer therapy and then respond will not be included as responders. More details on the derivation of composite response may be provided in in a separate programming guidance document if deemed necessary.

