#### **4.16.2 Composite Response Rate (Cohort B)**

Composite Response Rate (CRR) is defined as the percentage of participants who have a composite response as defined in [section 4.9.9](#). The composite response rate will be calculated for molecularly eligible centrally confirmed evaluable for response set as well as evaluable for response set.

Data obtained up until progression, or last evaluable assessment in the absence of progression, will be included in the assessment of CRR. Participants who discontinue study treatment without progression, receive a subsequent anti-cancer therapy and then response will not be included as responders in the CRR (i.e. both visits contributing to a response must be prior to subsequent therapy for the participant to be considered as a responder).

The CRR will be based on the investigator RECIST data and all scans regardless of whether they were scheduled or not.

Summaries will be produced that present the number and percentage of participants with a composite response. A two--sided 80% confidence interval using Clopper-Pearson method will be computed for response rate.

A by module, by cohort, by subject (subject identifier, centrally confirmed NGS result and IHC level) listing of composite response components (best overall radiological response, CTC conversion status, PSA decline, overall composite response, etc) will be provided.

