#### **4.17.6 Percentage of CTC count conversion from unfavourable to favourable (Cohort B)**

Conversion of CTC count is defined as a change from unfavourable at baseline ( $CTC \geq 5/7.5$  mL blood) to favourable at post-baseline ( $CTC < 5/7.5$  mL blood). Post-baseline result will be confirmed with a second consecutive value obtained three or more weeks later prior to radiological progression. Participants who discontinue study treatment without progression, receive a subsequent anti-cancer therapy and then respond will not be included as responders. The percentage of participants with CTC count conversion will be presented on those with unfavourable CTC at baseline. Summaries will be produced that present the number and percentage of participants with a CTC conversion for molecularly eligible and centrally confirmed evaluable for response set and evaluable for response set. A two-sided 80% confidence interval using Clopper-Pearson method will also be computed.

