**4.17.7 Confirmed PSA decline (Cohort B)**

Confirmed PSA decline is defined as a PSA reduction greater than 50% from baseline which is confirmed later by a second consecutive measurement done at least three weeks later prior to radiological progression. Participants who discontinue study treatment without progression, receive a subsequent anti-cancer therapy and then respond will not be included as responders. The proportion of participants with confirmed PSA decline will be presented on the molecularly eligible and centrally confirmed set and safety analysis set. Summaries will be produced with the number and percentage of participants with confirmed PSA decline at DCO and a two-sided 80% confidence interval using Clopper-Pearson method.

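### SAP sections 4.9.7 and 4.17.6 define confirmed CTC conversion differently: only 4.17.6 requires the confirming value to precede radiological progression.

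*SAP*

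**What the plan says.** Two sections of the SAP define CTC conversion for Cohort B.

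- **Section 4.9.7** describes the change from unfavourable to favourable and continues: "as per PCWG3 criteria) prior to radiological progression. Post-baseline result will be confirmed with a second consecutive value obtained three or more weeks later". The progression limit belongs to the change. The confirming value has its own sentence, with a minimum gap of three weeks and no latest time.
- **Section 4.17.6** gives the change with no progression limit and places the limit on confirmation: "Post-baseline result will be confirmed with a second consecutive value obtained three or more weeks later prior to radiological progression".

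Neither section refers to the other or says which one governs.

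The neighbouring rules are these.

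- **Section 4.9.9 (composite response)** counts the radiological, CTC and PSA outcomes "if any of these occur in the absence of radiological or PSA progression". Its CTC component is "confirmed by a second consecutive value obtained 3 or more weeks later" and its PSA component is "confirmed by a second consecutive measurement at least 3 weeks later (based on PCWG1 criteria". Neither component states a latest time for the confirming value.
- **Section 4.16.2 (composite response rate)** uses data only up to progression and adds that "both visits contributing to a response must be prior to subsequent therapy for the participant to be considered as a responder".
- **Section 4.17.7 (PSA decline)** requires the confirming PSA value to come before radiological progression. On later treatment it says: "Participants who discontinue study treatment without progression, receive a subsequent anti-cancer therapy and then respond will not be included as responders".
- **Section 4.17.6** has the same sentence on later treatment for CTC, excluding those who "receive a subsequent anti-cancer therapy and then respond will not be included as responders". Like 4.17.7, it does not add that both contributing values must precede the new therapy.

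**The concern.** Confirmed CTC conversion is a listed secondary endpoint and also one of the three routes to composite response. Confirmation is there to show that a favourable count persisted while the disease was controlled on ceralasertib. A confirming value taken after radiological progression does not show that.

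Two programmers, one working from 4.9.7 and the other from 4.17.6, could classify the same participant differently. Section 4.17.6 is the narrower rule, so any disagreement goes one way: the 4.9.7 rate is equal to or higher than the 4.17.6 rate.

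There is a second, smaller consequence. Section 4.16.2 calls for a listing by participant of CTC conversion status next to overall composite response. If the CTC flag is built from 4.9.7, a participant could be listed as a converter but not as a composite responder, purely because the two rules differ.

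**Working it through.** The SAP states no figure for this endpoint that could be reproduced, and its sample-size assumptions are redacted. The check is a comparison of the rules, followed by arithmetic for scale.

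**Step 1: the rules in terms of dates.** Let t1 be the date of the first favourable CTC value, t2 the date of the confirming value (t2 at least 21 days after t1), and tP the date of radiological progression.

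| Rule | Condition on progression |
|---|---|
| 4.9.7 | t1 before tP; t2 unrestricted |
| 4.17.6 | t2 before tP (so t1 is too) |
| 4.16.2 (composite) | only data up to progression used, so both before it |

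Sections 4.9.7 and 4.17.6 disagree exactly when t1 falls before tP and t2 does not.

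**Step 2: can that happen?** Take an illustrative participant with CTC 8 at baseline and 2 on Day 29, progression on a Day 52 scan, and CTC 3 on Day 57.

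- The scan is in window: Table 3 puts week 8 at Day 57, and ±7 days gives Day 50 to Day 64.
- The CTC gap is 57 − 29 = 28 days, which is more than 21.
- The participant is a conversion under 4.9.7 and not under 4.17.6.

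The draw days are assumed, because the SAP gives no CTC schedule.

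The bone rule offers another route. Section 4.9.4 requires a confirmatory scan at least 6 weeks later but dates progression to the scan that first documents the second new lesion. A confirming CTC value drawn between the two scans becomes post-progression in retrospect. The 6-week interval is longer than the 3-week CTC minimum, so there is room for this, again provided CTC is drawn in that interval.

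**Step 3: scale.** The inputs are:

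- Cohort B size 27 (Table 1).
- Denominator restricted to unfavourable baseline CTC (4.17.6).
- Section 3.1.1 aims for approximately 50% or more with unfavourable counts: 0.5 × 27 = 13.5, taken as 14. This is an assumption; the upper bound is 27.
- Two-sided 80% Clopper-Pearson intervals (4.17.6).

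The shift for one participant is 100/14 = 7.1 points, or 100/27 = 3.7 points.

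| Illustrative count | Rate | 80% CI |
|---|---|---|
| 4/14 | 28.6% | 13.1 to 49.2 |
| 5/14 | 35.7% | 18.5 to 56.3 |
| 5/27 | 18.5% | 9.3 to 31.7 |
| 6/27 | 22.2% | 12.1 to 35.8 |

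If 0 to 2 participants are affected (an assumption), the total shift is 0 to 14.3 points at n = 14 (2/14) and 0 to 7.4 points at n = 27 (2/27).

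**Step 4: later therapy.** Sections 4.16.1, 4.16.2 and 4.17.4 follow the exclusion sentence with an explanatory clause that both visits must precede subsequent therapy. Sections 4.9.9, 4.17.6 and 4.17.7 carry essentially the same sentence without the clause. This is missing explanation, not an opposite rule.

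**The case against.** The strongest reply is that 4.9.7 is a general definition that says nothing about late confirmation, whereas 4.17.6 is the analysis section for the endpoint and states the limit. Applying 4.17.6 satisfies both, so the mismatch is editorial. Part of this stands: following 4.17.6 breaks nothing in 4.9.7. But the SAP does not say that 4.17.6 governs, and 4.9.7 does include a progression limit and attaches it to a different value. It is therefore not simply silent.

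It can also be said that nobody may be affected, because CTC may not be collected after progression. That stands. The schedule is not in this document, and the effect may be nil.

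Three stronger readings are tempting, and the document does not support them.

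- **A reader might infer that a PSA decline confirmed after radiological progression could count.** Section 4.17.7 places the confirming PSA value before radiological progression, and 4.16.2 stops at progression. Only 4.9.9 read in isolation leaves the point open.
- **A reader might infer that the primary composite rate is exposed in the same way.** Section 4.9.9 requires absence of radiological or PSA progression, and 4.16.2 limits the data and requires both visits before new therapy. Some looseness remains: 4.16.2 takes its definition from 4.9.9, does not name the type of progression, and 4.9.9 leaves further detail to an optional programming document.
- **A reader might infer that 4.17.6 and 4.17.7 allow confirmation on the next therapy.** The clause in 4.16.1, 4.16.2 and 4.17.4 is worded as an explanation of the same exclusion, and these endpoints are defined as confirmed responses. Someone confirmed only on new therapy can fairly be said to have responded after starting it.

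**Conclusion.** The inconsistency between 4.9.7 and 4.17.6 is real and confined to one Cohort B secondary endpoint. A conversion first seen before radiological progression and confirmed only after it is a response under one definition and not under the other, and the looser definition can only raise the rate.

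The size is 7.1 points per affected participant with 14 in the denominator, or 3.7 points with 27. The 14 is assumed, the number affected is unknown and may be zero, and any effect depends on CTC being drawn after progression. The illustrative intervals before and after a one-participant change overlap heavily, and section 4.10 plans no formal hypothesis test, so this would shift a descriptive estimate and not a test result.

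The primary composite is largely protected, PSA confirmation after radiological progression is already excluded, and the wording on later therapy needs tidying but contains no contradiction. The correction is worth making because it is specific and cheap and settles the classification before the data are programmed.

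**What to change.** 1. Reword 4.9.7 so that both the first favourable CTC value and the confirming value must precede radiological progression, matching 4.17.6, and cross-refer the two sections.
2. For consistency, carry the clause already in 4.16.2, on both contributing visits preceding subsequent therapy, into 4.17.6 and 4.17.7.
3. State in 4.9.9 that, for each component, both contributing values must precede radiological progression, PSA progression and subsequent therapy. PSA progression has to be named because 4.9.9 already imposes it. It applies to the composite and not to the CTC and PSA secondary endpoints, so a listing in which a component and the composite differ for that reason is by design.

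The cost is a few words in four sections and one programming condition. Sample size does not change. The CTC and PSA rates may be slightly less favourable than under the looser reading.

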**4.9.8 PSA progression using PCWG3 criteria.**

The PSA progression is defined as a 25% or greater increase and absolute increase of  $\geq 2$ ng/ml above the nadir beyond 12 weeks. This must be confirmed by a second consecutive measurement value obtained at least 3 weeks later but within 12 weeks.

**4.9.9 Composite response**

Composite response will be defined on the basis of the following outcomes; if any of these occur in the absence of radiological or PSA progression (according to RECIST 1.1 for soft tissue and visceral

lesions, PCWG3 criteria for bone lesions, and PSA) participants will be considered to have responded:

- Investigator assessed radiological objective response by RECIST 1.1 for soft tissue and visceral lesions and PCWG3 criteria for bone lesions. Response must be confirmed at least 4 weeks later. Blinded Independent Central Review (BICR) assessment may be introduced if the cohort is expanded, subject to a protocol amendment.
- Conversion of CTC count from  $\geq 5/7.5\text{mL}$  blood (unfavourable) at baseline to  $< 5/7.5\text{mL}$  blood (favourable) (as per PCWG3 criteria) confirmed by a second consecutive value obtained 3 or more weeks later.
- PSA decline of  $\geq 50\%$  confirmed by a second consecutive measurement at least 3 weeks later (based on PCWG1 criteria).

For visits with non-evaluable radiological response, absence of radiological progression for that specific visit can be decided if there is any subsequent evaluable non progression response (CR/PR/SD). For visits with missing PSA assessment, absence of PSA progression for that specific visit can be decided if there is any subsequent non progressive PSA assessment available. Participants who discontinue study treatment without progression, receive a subsequent anti-cancer therapy and then respond will not be included as responders. More details on the derivation of composite response may be provided in in a separate programming guidance document if deemed necessary.

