**Table 4: Analysis set**

Analysis set	Definition
Enrolled analysis set	All study participants who signed the informed consent form (including screening failures).
Evaluable for response set	Cohort A: All study participants with measurable baseline disease who received at least 1 dose of study intervention.  Cohort B: All study participants with measurable disease and/or unfavourable CTC count at baseline who received at least 1 dose of study intervention.
[a] Molecularly eligible centrally confirmed set	All molecularly eligible and centrally confirmed participants who received at least 1 dose of study intervention.

[a]Molecularly eligible centrally confirmed evaluable for response set
	
Cohort A: All molecularly eligible and centrally confirmed study participants with measurable baseline disease who received at least 1 dose of study intervention.
 
Cohort B: All molecularly eligible and centrally confirmed study participants with measurable disease and/or unfavourable CTC count at baseline who receive at least 1 dose of study intervention.

CCI [REDACTED]
	
CCI [REDACTED]

CCI [REDACTED]
	
CCI [REDACTED]

Safety set
	
All participants who received at least 1 dose of study intervention.

Interim analysis set
	
All participants in the molecular eligible centrally confirmed evaluable for response set with a chance to have at least two follow up RECIST assessments (i.e. all patients who received first dose of ceralasertib, at least 16 weeks prior to the data cut off date).

[a] Please refer to the latest CSP for more details regarding central confirmation. A separate specification document will be provided to support the programming of the ‘centrally confirmed’ flag.

Upon database release, protocol deviation and analysis set outputs will be produced and will be sent to AZ for review. Prior to database lock, analysis set classification meeting will be arranged to discuss the outputs and decide which participants and/or participant data will be excluded from certain analyses. Decisions made regarding the exclusion of participants and/or participant data from analyses will be made prior to database hard lock and will be documented and approved by AZ.

A summary on which analysis set will be used for each outcome variable is provided in [Table 5](#) (Cohort A) and [Table 6](#) (Cohort B).

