**Table 11: Overall Radiological Visit Response**

Overall visit soft tissue response (RECIST 1.1)	Bone progression status (PCWG3)	Bone lesions at visit Present/Absent	Overall radiological visit response
CR	Non-PD	Absent	CR
CR	Non-PD	Present	PR
CR	NE	-	PR
PR	Non-PD or NE	Any	PR
SD	Non-PD or NE	Any	SD
NED	Non-PD or NE	Any	Non-PD
NE	Non-PD or NE	Any	PD
PD	Any	Any	PD
Any	PD	Any	PD

CR = complete response; NE = not evaluable (only relevant if a follow-up bone scan is not performed); NED = no evidence of disease (only relevant where there is no TL and NTL from baseline); PD = progressive disease; PR = partial response; SD = stable disease.

Confirmation of response (CR or PR) should be performed at the next scheduled RECIST and PCWG3 assessment (and must not be less than 4 weeks later) following the date the criteria for response were first met (see [Table 12](#)).

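### Section 4.9.9 leaves Non-PD out of the results that can clear a non-evaluable radiological visit, and Table 11 codes such a visit as PD, so some CTC or PSA responses in participants without soft-tissue lesions may be lost

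*SAP*

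**What the plan says.** Section 4.9.9 accepts a radiological response, a CTC conversion or a PSA decline as a composite response "if any of these occur in the absence of radiological or PSA progression". For a visit with a non-evaluable radiological response it adds that "absence of radiological progression for that specific visit can be decided if there is any subsequent evaluable non progression response (CR/PR/SD"). The parallel sentence for a missing PSA value accepts any later PSA result that is not progressive and gives no list.

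Table 11 combines soft-tissue and bone results into one radiological visit result. For participants without soft-tissue disease the row reads "NED Non-PD or NE Any Non-PD", and the footnote explains "NED = no evidence of disease (only relevant where there is no TL and NTL from baseline"). The next row, for a non-evaluable soft-tissue result, reads "NE Non-PD or NE Any PD".

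Table 4 defines the Cohort B evaluable-for-response set as "All study participants with measurable disease and/or unfavourable CTC count at baseline who received at least 1 dose of study intervention". The molecularly eligible, centrally confirmed version of the set uses the same baseline condition.

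The censoring text in section 4.9.6 describes participants without progression as those "who have a CR, PR, or SD by RECIST 1.1, and non-progressive for bone disease by PCWG3". Section 4.17.8 says much the same.

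**The concern.** A participant with no target or non-target lesion at baseline can qualify for the primary analysis set through an unfavourable CTC count. That participant cannot have a radiological CR or PR and can respond only through CTC or PSA. Those are the components for which the non-evaluable-visit rule matters, and the rule names three results that this participant can never produce.

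The composite response rate is the Cohort B primary endpoint (section 4.16.2) and the basis of the futility guidance (section 4.14). Any loss would run in one direction, downward, and would fall on one subgroup. With 27 participants at the primary analysis and 12 at the interim, a single responder is visible in the estimate.

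**Working it through.** The SAP states no figure on this point, so the check is a comparison of the rules, with simple arithmetic for scale.

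**1. Table 11 results against the list in section 4.9.9**

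| Soft tissue | Bone status | Overall result | Listed in 4.9.9 |
|---|---|---|---|
| CR | Non-PD, no bone lesions at the visit | CR | yes |
| CR | Non-PD with bone lesions, or NE | PR | yes |
| PR | Non-PD or NE | PR | yes |
| SD | Non-PD or NE | SD | yes |
| NED | Non-PD or NE | Non-PD | **no** |
| NE | Non-PD or NE | PD | no, printed as progression |
| PD in either component | | PD | no |

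Table 11 has four non-progression results: CR, PR, SD and Non-PD. Section 4.9.9 lists three of the four. The missing one is the only non-progression result in the NED row.

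**2. Who is affected.** Participants with non-target lesions only are not. Table 9 gives them CR or SD when they have not progressed, and both are listed. The gap is confined to participants with neither kind of lesion.

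**3. What triggers it.** A missing bone scan alone does not, because NED with bone NE is already Non-PD. The trigger is a soft-tissue assessment that cannot be evaluated. Section 4.9.1 assigns NE to such an assessment unless there is evidence of progression.

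**4. What happens at such a visit.** Suppose the week 8 soft-tissue assessment is not evaluable, a CTC or PSA response is seen at that visit, and week 16 gives Non-PD.
- Under section 4.9.9 read literally, the week 16 Non-PD is not on the list, so week 8 is not cleared.
- Under Table 11 as printed, week 8 is already PD, and the rule in section 4.9.9 is never reached.

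The second step conflicts with section 4.9.9 and with Table 12. Both presuppose that a non-evaluable overall radiological result exists, yet no row of Table 11 produces one. Adding Non-PD to the list without settling that row would therefore recover nobody in this example.

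**5. Scale per participant.** Inputs: 27 and 12 participants (Table 1); two-sided 80% Clopper-Pearson interval (section 4.16.2).
- Primary analysis: 1/27 = 3.7 percentage points.
- Interim: 1/12 = 8.3 percentage points.

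Illustration with assumed responder counts, one response recovered:

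| n | Without it | With it |
|---|---|---|
| 27 | 5/27 = 18.5% (80% CI 9.3 to 31.7) | 6/27 = 22.2% (12.1 to 35.8) |
| 12 | 2/12 = 16.7% (4.5 to 38.6) | 3/12 = 25.0% (9.6 to 47.5) |

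The total loss cannot be computed. The SAP gives neither the number of participants without soft-tissue lesions nor the frequency of non-evaluable visits.

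**The case against.** The strongest reply is that Non-PD is by its name a non-progression response, so the bracket merely gives examples. The sentence is permissive, does not say that only these results count, and does not say that an uncleared visit makes someone a non-responder. Section 4.9.9 also foresees a programming guidance document. This reading is possible. But the bracket is an explicit list, the neighbouring PSA sentence has none, and a programmer would code what is listed. The guidance document is optional and lies outside the SAP. A primary endpoint should not depend on it.

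A second reply is that the trigger is narrow. With no target or non-target lesions, both lesion responses are not applicable, and section 4.9.1 says that an unanswered new-lesion question should not overtly affect the derivation. That limits the frequency, and this part stands. It does not empty the case: section 4.9.1 still gives NE to a tumour assessment that cannot be evaluated, and Table 9 has no row for a participant with neither lesion type.

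Several stronger readings are tempting and are not supported:
- *Missed visits trigger the same loss.* Section 4.9.6 separates missed visits from NE visits, and the radiological sentence in section 4.9.9 speaks only of non-evaluable ones. Extending it to missed visits is an assumption.
- *rPFS is affected too.* The wording in sections 4.9.6 and 4.17.8 omits this group, but the operative condition is absence of progression, and censoring may use the last bone scan with fewer than two new lesions. No rPFS value is shown to change.
- *Every such responder is lost.* A CTC or PSA response that continues to a later evaluable Non-PD visit may still count.
- *The futility decision is compromised.* Section 4.14 calls the stopping rule guidance only, subject to sponsor review of all data, and its threshold is redacted.

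**Conclusion.** The point holds in a limited form. The list in section 4.9.9 omits the only non-progression result available to Cohort B participants with no target or non-target lesions at baseline. Read literally, a CTC or PSA response at a visit with a non-evaluable soft-tissue assessment cannot be cleared by a later Non-PD. The NE row of Table 11 is a further obstacle, because it calls that visit PD first.

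The possible loss is 3.7 percentage points per participant at n = 27 and 8.3 at n = 12, always downward. This rests on two assumptions: that the bracket is coded as written, and that the response does not also qualify at a later evaluable visit. The number affected is probably small, but the SAP gives no basis for a count. A reader might infer an established downward bias in the composite response rate; the document supports only the possibility. It is still more than clerical, since it concerns who counts as a responder on a primary endpoint.

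**What to change.** - In section 4.9.9, extend the bracket to CR/PR/SD/Non-PD.
- In the same edit, reconcile the NE row of Table 11 with section 4.9.9 and Table 12, so that the plan says in one consistent way what overall result a non-evaluable soft-tissue visit receives. Without this the first change has no effect for NE visits.
- Optionally, tidy the explanatory wording in sections 4.9.6 and 4.17.8 so that it also covers participants with no soft-tissue disease. This is for consistency only.

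The cost is a few lines of text and the matching derivation code. No new data are needed.
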